9.3 Schedule of Events

	Schedule of Events
--	---------------------------

Study Activity	Visit 1	Visit 2
Tetraphraph		X
Informed consent	X	
Review of Medical Record	X	
Adverse event evaluation		X

10 Statistical Plan

10.1 Sample Size Determination

Based on Pearson correlation test, 50 patients will allow us to detect the correlation of 0,6 or greater between cardiac output and the time of recovery after reversal with sugammadex with a power greater than 90% and a significance level of 0.05.

10.2 Statistical Methods

Continuous variables will be summarized as mean (standard deviation) or median (range) while categorical variables will be reported as frequency (percentage). Pearson correlation or Spearman correlation will be used to test 1) the correlation between cardiac output and the time of recovery after reversal with sugammadex and 2) the correlation between age and the time of recovery. Linear regression model will be used to estimate the change of recovery time per unit change in cardiac output or age. If time to recovery does not follow a normal distribution, log transformation will be performed before analysis. All test are two-sided with alpha level set of 0.05 for statistical significance.

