12.6	DATA SECURITY AND CONFIDENTIALITY	18
12.7	DATA QUALITY ASSURANCE	18
12.8	DATA CLARIFICATION PROCESS	18
12.9	RECORDS RETENTION.....	18
13	STUDY MONITORING, AUDITING, AND INSPECTING	18
13.1	STUDY MONITORING PLAN.....	18
13.2	AUDITING AND INSPECTING	18
14	ETHICAL CONSIDERATIONS.....	19
15	STUDY FINANCES.....	19
15.1	FUNDING SOURCE	19
15.2	CONFLICT OF INTEREST.....	19
15.3	SUBJECT STIPENDS OR PAYMENTS	19
16	PUBLICATION PLAN	19
17	REFERENCES.....	20
18	LIST OF IN-TEXT TABLES.....	20
18.1	SCHEDULE OF EVENTS	20
18.2	INTRAOPERATIVE DATA	21
19	LIST OF IN-TEXT FIGURES.....	24
19.1	TETRAGRAPH.....	24

1 Protocol Approval Form

Protocol Number: 20-001771

Study Name: Correlation between cardiac output and recovery time after reversal of rocuronium-induced blockade with sugammadex

This protocol has been reviewed and approved by the following:

J. [name]
Principal Investigator

17/Aug/2022

Date

2 List of Abbreviations

AE	Adverse Event/Adverse Experience
AMG	Acceleromyography
CE	Conformite Europeene
CFR	Code of Federal Regulations
cMAPs	Compound Muscle Action Potentials
CO	Cardiac Output
CRF	Case Report Form
CTSA	Center for Translational Science Activities
DSMB	Data and Safety Monitoring Board
EHR	Electronic Health Record
EMG	Electromyography
FDA	Food and Drug Administration
GCP	Good Clinical Practice
HIPAA	Health Insurance Portability and Accountability Act
IB	Investigator's Brochure
ICU	Intensive Care Unit
IRB	Institutional Review Board
KMG	Kinemyography
MMG	Mechanomyography
NMBA	Neuromuscular Blocking Agent
Non-UPIRTSO	Non-Unanticipated Problems Involving Risk to Subjects or Others
PACU	Post Anesthesia Care Unit
PHI	Protected Health Information
PI	Principal Investigator
PTC	Post-tetanic Potentiation
SAE	Serious Adverse Event/Serious Adverse Experience
SGX	Sugammadex
SOP	Standard Operating Procedure
TOF	Train-of-four
TOFC	Train-of-four count
TOFR	Train-of-four ratio
UPIRTSO	Unanticipated Problems Involving Risk to Subjects or Others
VNRS	Verbal Numeric Rating Scale

3 Study Summary

Title	Correlation between cardiac output and recovery time after reversal of rocuronium-induced blockade with sugammadex
Running Title	CO and Sugammadex
Phase	N/A
Methodology	Open-Label
Overall Study Duration	6 months
Subject Participation Duration	2 – 5 hours
Single or Multi-Site	Single site
Objectives	The primary aim of this study is to correlate the temporal relationship between cardiac output and clinical recovery of neuromuscular block affected by sugammadex.

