6.3 Duration of Participation

2-5 hours, depending on duration of surgery

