6.4 Primary Study Endpoints

The primary endpoint of the study will be to examine the correlation between cardiac output and the time of recovery after reversal with sugammadex as measured by TOFR ≥ 0.9 .

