6.6 Identification of Source Data

The study data points will be recorded on the developed Case Report Forms (CRFs) by the study team members. In addition to the data collected intraoperatively, several intraoperative characteristics will also be extracted from the medical record ([Table 18.2](#)). These will include type and total dose of NMBA used, time and dose of last NMBA administration, time and dose of specific reversal agent administration, time of tracheal extubation, and TOF ratio at the time of extubation (if available).

7 Subject Selection Enrollment and Withdrawal

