7.3 Subject Recruitment, Enrollment and Screening

On a daily basis, there are over 20 elective surgical cases performed at Mayo Clinic in Florida and thus no difficulties in accrual are anticipated based on historical volumes. We will target at least 3 participants per week to complete this study. The initial accrual period will last at least 3 months followed by interim analysis and additional time for accrual will be determined to meet the target. Patients will be provided with a Research Participant Consent and Privacy Authorization Form describing the study devices, protocol, inclusion and exclusion criteria, as well as risks and benefits of participation.

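### Does the plan have to name which cardiac output value enters the primary correlation?

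*Combined protocol and SAP*

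**What the plan says.** The Study Summary (section 3) sets out to "correlate the temporal relationship between cardiac output and clinical recovery of neuromuscular block affected by sugammadex". Section 6.4 reads: "The primary endpoint of the study will be to examine the correlation between cardiac output and the time of recovery after reversal with sugammadex", with recovery defined by a TOF ratio of at least 0.9. Section 10.1 claims that "50 patients will allow us to detect the correlation of 0,6 or greater between cardiac output and the time of recovery", at more than 90% power and a significance level of 0.05. Section 10.2 uses Pearson or Spearman correlation "to test 1) the correlation between cardiac output and the time of recovery after reversal with sugammadex" and adds: "Linear regression model will be used to estimate the change of recovery time per unit change in cardiac output or age". It calls for a log transformation if recovery time is not normally distributed.

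On collection, sections 8.1 and 9.2 say CO is measured continuously through the pulmonary artery catheter, and 9.2 takes the values from the electronic record. Table 18.2 has a CO column against these rows: calibrated baseline, TOF count of zero after the first relaxant dose, pre-sugammadex, every 20 seconds from +20 to +300, and extubation. Section 6.3 gives participation as "2-5 hours, depending on duration of surgery".

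**The concern.** A correlation needs one CO number per patient, and the plan collects many. Section 9.2 puts the baseline row before the relaxant and the pre-reversal set near the end of surgery, so two cells on the same form may be hours apart. An early reading would be a noisier stand-in for CO at reversal. It would weaken the correlation, flatten the regression slope, and could take power below the figure in 10.1.

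There is also a risk of choosing with results in view. The study is open-label, and section 7.3 says: "The initial accrual period will last at least 3 months followed by interim analysis", without saying what that analysis covers. If the CO value were picked there because it gave the smallest p-value, the 5% error rate would not hold.

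Three smaller gaps seem to add to this. The list in section 6.6 ("These will include type and total dose of NMBA used, time and dose of last NMBA administration") does not mention CO, the schedule in 9.3 has no CO line, and 10.2 gives no rule for choosing Pearson or Spearman.

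**Working it through.** **Inputs.** n = 50, r = 0.6 and alpha 0.05 (section 10.1), two-sided (section 10.2). The form rows are in Table 18.2. The correlation between a reading taken at another time and CO at reversal, called k below, is not in the documents; 0.9, 0.7 and 0.5 are assumed.

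**The plan's own figure.** By Fisher's z, power = Phi(atanh(r) × sqrt(n − 3) − 1.960).
- atanh(0.6) = 0.693 and sqrt(47) = 6.856. Their product is 4.752; 4.752 − 1.960 = 2.792; power = 99.7%. Simulation of the t-test gives the same.
- Smallest r with 90% power: tanh((1.960 + 1.282) / 6.856) = tanh(0.473) = 0.44.
- n for 90% power at r = 0.6: (3.242 / 0.693)² + 3 = 24.9, so 25 patients.

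Section 10.1 is right, and 50 is twice the number needed at r = 0.6.

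**If another reading were used.** Suppose r = 0.6 belongs to CO at reversal, and the other reading relates to recovery only through CO at reversal. Expected r is then 0.6 × k.

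| k | Expected r | Power, n = 50 |
|---|---|---|
| 0.9 | 0.54 | 98.5% |
| 0.7 | 0.42 | 86.6% |
| 0.5 | 0.30 | 56.4% |

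Power stays at 90% while k is at least 0.44 / 0.6 = 0.73. With equal SDs the slope shrinks by the factor k. A mean of many equally correlated readings has correlation sqrt(k) with CO at reversal (0.95, 0.84, 0.71) and simulated power of 99.4%, 96.9% and 88.1%.

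Two analysts, one using CO at reversal and one using the other reading, would disagree on significance in a simulated 1.2%, 12.6% or 42.5% of studies. These are almost the power differences (99.7 − 98.5 = 1.2; 99.7 − 86.6 = 13.1; 99.7 − 56.4 = 43.3), so they are not separate evidence.

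**If the reading were picked by its p-value.** With no true association and three readings correlated 0.9, 0.7 or 0.5 with one another, simulated type I error is 8.4%, 11.0% or 12.8% if picked at the end. It is 8.0%, 10.2% or 11.8% if picked at 39 patients and tested on all 50. The 39 is 3 per week × 13 weeks; section 7.3 gives both the rate and the period as minimums. Choosing only between log-scale Pearson and Spearman gives 6–7%. Either one fixed in advance holds 5%.

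**Which reading the documents point to.** The form has 3 + 15 + 1 = 19 timed rows. From pre-sugammadex onward there are 1 + 15 + 1 = 17; only two come earlier. The aim and endpoint concern recovery after sugammadex. The documents do not say when the catheter is placed, only that it is used during surgery, so a CO value before the first relaxant dose may not exist for every patient.

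**The smaller gaps.** The list in 6.6 is introduced as examples and refers to Table 18.2, which has the CO column. Section 9.2 names the electronic record as the source, and 12.4 says record data are transcribed to the case report form, so the source is settled. CO is standard-of-care monitoring, so its absence from a four-line schedule shows little. Section 10.2 does give a condition for the log step, non-normality; only the criterion for judging it is missing. The Pearson sizing and the linear regression both point to Pearson, which gives the same test as the regression slope.

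**The case for a change.** The strongest reply is that no sentence selects the pre-sugammadex row. The form treats every row alike, and section 4.2 justifies the study by a weakness in how earlier work measured CO, so this study in particular should say what its CO value is. Attenuation also needs no misconduct: an analyst who honestly fixed the baseline reading in advance would report a flatter slope. And some readings follow sugammadex; a mean taken up to the moment of recovery would have a window whose length depends on the outcome.

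The textual fact stands: the definition is not written. The warning about a window ending at recovery is sound, and a careful analyst would avoid it. What does not stand is the step from an unwritten definition to a likely wrong result. The large losses need the early reading to be used, a k that the documents do not supply, and no link between that reading and recovery except through CO at reversal. The selection figures need a pick by smallest p-value, which no section suggests; the interim sentence in 7.3 is about accrual time. Among readings minutes apart around reversal, k of 0.9 or more is plausible (also an assumption), and power is then about 98.5% or higher.

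**Conclusion.** The documents leave the CO time point or summary unwritten, and analysts would fill that gap sensibly with CO at reversal. The power statement in 10.1 is conditional on r = 0.6, reproduces at 99.7%, and tolerates a fall in the true correlation to about 0.44. The lower power (87% and 56%), the disagreement rates and the 8–13% error rates are illustrations under assumed correlations between readings, not findings about this plan. In a single-site observational study that calls itself a pilot, recording the choice before the data are analysed is ordinary good practice; it would correct no rule or figure in the plan. No change is called for.

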4.1 Abstract

Sugammadex has been introduced into the market as a fast-acting selective relaxant binding agent to reverse rocuronium-induced neuromuscular block. Several studies have shown that longer times are required in older patients to recover from rocuronium-induced neuromuscular block, which is likely related to age-related decreases in cardiac output. The aim of this study is to evaluate the correlation between cardiac output and speed of reversal of rocuronium-induced neuromuscular block with sugammadex in patients.

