4.2 Background

Neuromuscular blocking agents (NMBAs) are a class of medications routinely used during anesthesia to facilitate endotracheal intubation (1), and improve conditions for optimal surgery (2). Routine reversal of neuromuscular blockade is very common in order to return patients' spontaneous breathing and prevent residual blockade and all the associated complications (3, 4). Sugammadex, a novel γ -cyclodextrin, is a unique neuromuscular reversal drug discovered by Anton Bom. It is the first in a new class of selective relaxant binding agents, and it was designed to rapidly reverse rocuronium-induced neuromuscular block (5, 6). Sugammadex-rocuronium interaction reduces the amount of free muscle relaxant in the plasma, reducing the level of free NMBA at the neuromuscular junction (7). Some studies have shown that longer times are required in older patients to recover from rocuronium-induced neuromuscular block (8). Suzuki et al, showed that achieving a TOFR of 0.9 was slower in older than younger patients. In addition, Yoshida et al (9), reported that in elderly patients (65 years or older), the time to reach a TOFR of 0.9 following 2 mg/kg sugammadex was dependent on the cardiac output. These studies suggested that the slower duration to reach a TOFR of 0.9 in older patients is probably attributable to their lower cardiac output. However, they had a limitation and it was the technique they used to measure the cardiac output because compared with other invasive techniques, FloTrac/Vigileo tends to underestimate the cardiac output (10).

The purpose of this study is to determine the recovery time from rocuronium-induced blockade after reversal with sugammadex as a function of cardiac output in elderly and young patients. Cardiac output measurements will be performed pulmonary artery catheterization, which is passing a catheter into the right side of the heart and the arteries leading to the lungs to monitor heart function and blood flow pressures. It is important to highlight that pulmonary artery catheter would be part of the normal care and intraoperatively proceedings. Neuromuscular monitoring will be performed using TetraGraph (Senzime AB, Uppsala, Sweden) which is a standalone EMG-based quantitative monitor that is FDA approved. EMG measures electrical activity within the muscle following peripheral nerve stimulation and is unaffected by involuntary patient motion or restricted muscle movements from surgical positioning.

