4.3 Risks and Benefits

- The benefits of using neuromuscular blockade monitoring devices:
Early detection of optimal time for tracheal intubation; optimal management of intraoperative depth of neuromuscular block to facilitate surgical procedures; determination of appropriate time and dose of sugammadex reversal; and detection of residual neuromuscular blockade
- The risks of using neuromuscular blockade monitoring devices:
Slight discomfort when electrical stimulation is administered in awake volunteers; however, our patients will be anesthetized, rendering this risk as extremely minor.

5 Study Objectives

Primary Objective

To determine the recovery time from rocuronium-induced blockade after reversal with sugammadex as a function of cardiac output.

Secondary Objective

To determine the correlation between the speed of recovery from NMBA with sugammadex and age.

6 Study Design

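### Section 10.2 plans no model with cardiac output and age together, so the written analysis cannot show whether a cardiac output–recovery correlation persists after accounting for age

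*Combined protocol and SAP*

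**What the plan says.** Section 10.2 lists two bivariate tests, Pearson or Spearman: CO against recovery time, and age against recovery time. It then adds: "Linear regression model will be used to estimate the change of recovery time per unit change in cardiac output or age". It names no model with both terms, partial correlation, interaction, age stratum or covariate list. The only other analysis described, in section 10.4, is a sensitivity analysis for withdrawals.

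The objectives in section 5 are stated separately: recovery time as a function of CO (primary) and "To determine the correlation between the speed of recovery from NMBA with sugammadex and age" (secondary). The primary endpoint in section 6.4 is the CO–recovery correlation.

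The rationale joins the three variables. Section 4.1 says the longer recovery of older patients is something "which is likely related to age-related decreases in cardiac output". Section 4.2 says of the earlier work: "These studies suggested that the slower duration to reach a TOFR of 0.9 in older patients is probably attributable to their lower cardiac output". It gives this study's purpose as recovery time "as a function of cardiac output in elderly and young patients". Section 7.1 admits all adults, so age can vary widely, and the form in section 18.2 records both age and CO.

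**The concern.** If older patients have lower CO and also recover more slowly, a CO–recovery correlation can arise in three ways: because CO matters, because age matters through some other route, or both. Two separate marginal analyses look much the same in each case. What distinguishes them is the age–CO correlation, or equivalently a regression with both terms, and neither is planned.

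A significant primary result would support the statement that CO correlates with recovery time. It would not show whether that association is separate from age, or whether the age association shrinks once CO is in the model. Those are the questions that sections 4.1 and 4.2 raise, and readers could credit CO with an association that age carries.

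**Working it through.** **Inputs from the documents.** n = 50 and a detectable correlation of 0.6 in size (section 10.1); two-sided alpha 0.05 (section 10.2). The documents give no age–CO or age–recovery correlation, so those below are assumptions, shown over a range. C is CO, T is recovery time, A is age.

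**The plan's own figure.** Section 10.1 says that "50 patients will allow us to detect the correlation of 0,6 or greater" with power above 90%. By Fisher's z, power = Φ(atanh(0.6)·√47 − 1.96) = 99.7%, so the statement is correct. It concerns the unadjusted correlation only.

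**Formula for the adjusted correlation.** r(CT|A) = (r_CT − r_CA·r_AT) / √((1 − r_CA²)(1 − r_AT²)), tested by t on 47 degrees of freedom.

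**1. One planned output, different conclusions.** Suppose the planned analyses return r_CT = -0.40 (p=0.004) and r_AT = 0.50 (p=0.0002), each on 48 degrees of freedom.

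- r_CA = -0.3: (-0.40 + 0.15)/√(0.91 × 0.75) = -0.303, p=0.035.
- r_CA = -0.5: (-0.40 + 0.25)/√(0.75 × 0.75) = -0.200, p=0.168.
- r_CA = -0.6: (-0.40 + 0.30)/√(0.64 × 0.75) = -0.144, p=0.322.

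The planned output does not say which case applies.

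**2. How often the marginal CO test is significant if CO adds nothing beyond age.** Here r_CT = r_CA·r_AT. Simulated figures come from 40,000 trivariate normal trials of 50 patients.

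| r_CA | r_AT | Implied r_CT | Marginal test, Fisher z | Marginal test, simulated | Age-adjusted test, simulated |
|---|---|---|---|---|---|
| -0.3 | 0.4 | -0.12 | 13% | 13% | 5% |
| -0.5 | 0.5 | -0.25 | 42% | 42% | 5% |
| -0.6 | 0.6 | -0.36 | 73% | 74% | 5% |

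These are real marginal correlations that could be misattributed to CO. They are not type I errors of the planned test.

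**3. Whether 50 patients can support the joint model.** Set r_CT = -0.6, the size used in section 10.1. Adjusted power by Fisher z uses √(50 − 3 − 1) = √46.

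| r_CA | r_AT | Adjusted r | Power, Fisher z | Power, simulated |
|---|---|---|---|---|
| -0.3 | 0.4 | -0.549 | 99% | 99% |
| -0.5 | 0.5 | -0.467 | 93% | 94% |
| -0.6 | 0.6 | -0.375 | 76% | 77% |
| -0.7 | 0.6 | -0.315 | 60% | 60% |

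If instead age acts on recovery only through CO, as the rationale suggests, then r_AT = r_CA·r_CT. For r_CA = -0.3, -0.5, -0.6 and -0.7 this gives r_AT = 0.18, 0.30, 0.36 and 0.42, adjusted r = -0.58, -0.54, -0.51 and -0.47, and power 99%, 99%, 97% and 94%.

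**4. Precision cost.** For the same residual variance, the interval for the CO slope widens by 1/√(1 − r_CA²): 1.05, 1.25 and 1.40 at r_CA = -0.3, -0.6 and -0.7.

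**The case against.** The strongest reply is that no stated objective goes unanswered. Sections 5 and 6.4 ask for marginal relations and section 10.2 delivers them; nothing promises an age-independent CO effect. That stands. It is why the primary analysis should stay as it is and why this is a limit on interpretation, not an error in the primary test. It does not remove the gap, because the rationale and the purpose stated in section 4.2 bring age and CO together and the analysis does not.

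A second reply is that sections 4.1 and 4.2 describe age lowering CO, and CO slowing recovery. CO is then an intermediate, and the scenarios in which CO adds nothing beyond age contradict the protocol's own mechanism. It is fair to say that those scenarios are not what the rationale predicts. But the joint model is what tells the two patterns apart, and under the protocol's mechanism it has 94% to 99% power at n=50.

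Third, the regression sentence is loose and does not forbid both terms in one model, and the model could be fitted later as exploratory. True, but nothing commits to it, and a model chosen after the data are seen can be chosen for the answer it gives.

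Fourth, a two-term model leaves out sugammadex dose and the pre-reversal train-of-four measurements, although anesthetic management is discretionary (section 9.2) and section 18.2 records both. That also stands and should be stated in the report.

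**Conclusion.** The concern holds. The plan specifies only separate analyses of CO and age, and no section supplies a joint model or the age–CO correlation. The listed objectives and the sample size statement are unaffected. What is lost is any pre-specified basis for saying whether CO is associated with recovery beyond age, or how far CO accounts for the age association.

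The size of the problem depends on correlations the documents do not give. Across the assumed values, the same planned output allows an adjusted CO correlation that is significant or clearly not, and a CO with no association beyond age would still give a significant primary test in about 13% to 74% of trials. This should be corrected, since the remedy is cheap and changes what the study can conclude. That the joint model is missing is certain from the text; the percentages are illustrations.

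**What to change.** Leave the primary correlation as written. Add to section 10.2 one pre-specified secondary linear regression of recovery time (log-transformed if the existing rule calls for it) on CO and age together. Report:

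- the age-adjusted CO slope with its 95% confidence interval;
- the age slope with and without CO in the model;
- the age–CO correlation.

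Limit any statement that CO accounts for the age association to attenuation in this model, without causal wording. State that the model does not adjust for sugammadex dose or pre-reversal train-of-four measurements.

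The cost is SAP wording and one degree of freedom, with no new data and no change to the primary test or to n. The drawback is the loss of precision shown above when age and CO are strongly correlated, so the plan should also say that a non-significant adjusted slope will not be read as absence of association.
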